We will conduct a prospective epidemiological study to determine the effect of severe obesity on physical activity, sedentary behavior, and cardiometabolic risk factors among African American and White children and adolescents. Physical activity, sedentary behavior, cardiometabolic risk factors, and body composition will be assessed in each participant using gold standard, objective measures, with the first assessment (Year 0) in 2016-17 and the second assessment (Year 2) in 2018-19. We previously observed that children's physical activity and other health behaviors vary throughout the year based on school term versus school holiday.⁶⁰ Therefore, each child's Year 0 and Year 2 clinic visits will be scheduled at a consistent time of year to protect against changes due to the child being in school term or on a school holiday. Furthermore, we will use a scheduled enrollment to ensure that clinic visits are representative of both school term and school holidays.

Following an initial recruitment telephone screen or web-screen (followed by a telephone screen) to assess initial eligibility criteria, eligible participants will be scheduled for their Orientation visit at PBRC with their parent or legally authorized representative where participants will be formally oriented to the study by receiving detailed information on the purposes, goals, procedures, participant flow, and study timeline. Staff will obtain signed informed consent and child assent before participants take part in any of the study-related procedures. Participants will be given the GPS and accelerometer devices as well as instructions on how to wear them for the next week. Participants will also be given the EMA application on their personal cell phones or a provided mobile device along with instructions on how to respond to the prompts for the next week. Participants will be introduced to the ASA-24 dietary intake tool and provided instructions on how to complete two separate recalls from their home computer prior to the Year 0 clinic visit. Participants and parents may be asked to complete surveys on the devices while waiting. At the conclusion of the Orientation. Parents may receive reminders from staff for all tasks required of participants between orientation and Year 0.

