Participants will be fasting at the Year 0 visit. Measurements including anthropometry, blood draw, urine pregnancy test, body composition, dietary intake, activity monitor tracking equipment collection, and all remaining surveys will take place during the clinic visits. Participants must be accompanied by a parent or legally authorized representative at the clinic visits.

Approximately 10 days prior to the Year 2 visit, participants will pick up an accelerometer and GPS device to wear for 7 days and return at the Year 2 clinic visit. Participants will also be given instructions on how to complete two trials of the ASA-24 dietary intake tool from their home computer prior to the Year 2 clinic visit. Participants will return to clinic approximately 2 years (+/- 6 months) after their Year 0 visit for a Year 2 visit, in which all procedures collected during Year 0 will be repeated. **Table 2** includes a list of all measurements occurring at both visits. Parents may receive reminders from staff for all tasks required of participants between orientation and Year 2.

Measurements

	Orientation	Year 0	Year 2
Informed consent/assent	Х		
Anthropometry (Height, weight, waist size)		Х	Х
Blood Pressure		Х	Х
Body Composition (DXA, MRI)		Х	Х
Blood Draw		Х	Х
Urine Pregnancy Test (eligible females only)		Х	Х
Dietary Intake (ASA-24)		Х	Х
Family environment surveys		Х	Х
Neighborhood environment surveys		Х	Х
Body image and mood surveys		Х	Х
Global Positioning System (GPS)	7-days		7-days
Physical Activity (Actigraph GT3X+)	7-days		7-days
Ecological momentary assessment (eMA)	7-days		

Table 2. Study procedures

Description of tests and procedures

Anthropometry

Weight- Anthropometry will be measured to the nearest 0.1 cm (0.1 kg for weight). All measures are taken twice with the analyzed value being the average of both measurements. If the measures differ by greater than 0.5 units, a third measurement will be taken to replace the discrepant value. Participants wear only a hospital gown and undergarments while being weighed.

Height- Standing height will be measured using a Harpenden stadiometer (Holtain Limited, Crymych, UK). Participants will remove shoes, stand upright with heels and back against the stadiometer, inhale, and hold breath while an assessor provides traction to align the participant's head along the Frankfort Horizontal Plane during measurement. Weight will be measured using a Michelli GSE 460 scale (G.T. Michelli Co., Baton Rouge, LA).

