We expect challenges in following up with this cohort 2 years after the Year 0 clinic visit. We will employ several retention strategies between Years 0 and 2 that have been successful in prior trials, including mailing birthday cards to child participants, sending quarterly newsletters on family and children's health topics, inviting families to the annual Pennington Biomedical 5K, and telephoning the parent 2 months prior to the Year 2 clinic visit to schedule the visit and answer questions. The child will receive a stipend after each completed clinic visit and upon returning the accelerometer/GPS tracker, and the child will receive a certificate of completion upon finishing the study. Additionally, Pennington Biomedical has an excellent retention rate for clinical trials. The population of Baton Rouge is relatively stable, 82 and the majority of children will still be enrolled in K-12 school. Offering assessments during summer and school holidays will increase the likelihood of participation. We successfully followed up with children in prior prospective trials: 87% of children aged 10 to 14 years returned for a 2-year followup clinic visit in our Baton Rouge Children's Study (114 of the initial 131).77 Our retention for adult clinical trials is also excellent: we examined 14 trials conducted at Pennington Biomedical with a total of 1581 participants and observed a 70% retention rate over an average 4.8 year follow-up (range 1 year to 13 years). We expect an even higher retention rate due to the shorter follow-up time (2 years). Pennington Biomedical staff may contact participants every 3-6 months by phone or email to maintain contact between Year 0 and Year 2 clinic visits as well as schedule the Year 2 visit.

Anticipated Dropout

The 25% dropout rate is a combined estimate for both loss to follow-up and exclusions that occur during the clinic visit. Based on attrition at 2-year follow-up for Pennington Biomedical's Baton Rouge Children's Study,77 13% of the sample is expected to not report back for the 2-year follow up. An additional 12% is expected to be excluded due to exceeding weight limitations or the refusal of certain procedures (e.g. MRI, DXA) based on refusal rates in Pennington Biomedical's WAIST Study.20

Statistical Analysis

Objective 1:

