The hypotheses will be tested using a series of generalized linear models with severe obesity as the independent variable. First, linear mixed effect models will be used to test for effects between BMIz and each dependent continuous variable (change in: min/day sedentary behavior, min/day MVPA, and each cardiometabolic risk factor). Next, logistic regression models will be used to determine the association between BMIz with the likelihood of not meeting recommended behaviors (i.e. top quartile of min/day of sedentary behavior; MVPA < 60 min/day) or being at elevated cardiometabolic risk. Finally, the cohort will be stratified into two groups based on obesity at Year 0: severely obese (SO) and not severely obese (NSO). Logistic regression models will be used to determine associations between SO (vs. NSO) and each dependent variable (i.e. change in: minutes/day sedentary time, minutes/day MVPA, and each continuous cardiometabolic risk factor). Covariates will include age, sex, dietary intake, and race. School

term vs. school holiday will be considered as an additional covariate if time of year is significantly associated with the independent and dependent variables.

Secondary analysis will use MRI and DXA as covariates in the model (namely the visceral, trunk, and total body fat). These measurements, along with BMIz, may be highly correlated. Various variable select criteria (including LASSO and support vector machine) will be used to determine which combination of these variables best explains the variance in the data. The full model will enable the comparison of imaging-based body composition measures vs. BMIz alone and their associations with physical activity, sedentary behavior, and cardiometabolic risk factors in children.

As exploratory analyses, dietary intake will be tested as a potential mediator to explain significant associations between the predictor variable (BMIz) on outcomes (physical activity, sedentary behavior, and cardiometabolic risk factors). Series of sequential models will be used to test each pathway using a path analysis model based on the Baron and Kenny causal steps for mediation.73,74

Objective 2:

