Analyses to test Hypothesis 2 will be conducted using a series of linear regression models (i.e. linear mixed effects models). Based on difference score between Years 0 and 2 for total body fat, the group will be divided into two dichotomous groups using percentiles: high fat gainer (HFG) and low fat gainer (LFG). These variables will be used to predict changes in physical activity, sedentary behavior, and each cardiometabolic risk factor in linear mixed effect models. Covariates will include age, sex, dietary intake, and race. School term vs. school holiday will be considered as an additional covariate if time of year is significantly associated with the independent and dependent variables. Secondary analysis will use MRI and DXA as covariates in the model (namely the visceral, trunk, and total body fat). As previously reported, variable select criteria (including LASSO and support vector machine) will be used to determine which combination of these variables best explains the variance in the data. The full model will enable the comparison the accumulation of imaging-based body composition measures vs. BMIz alone and their associations with change in physical activity, sedentary behavior, and cardiometabolic risk factors in children. Finally, there are no standard accepted definitions of pediatric severe obesity to dichotomize participants based on MRI or DXA measures of body fat. Therefore, receiver operating characteristic curves will be created to estimate the value at which visceral, trunk, and body fat best correspond with the BMI definition of severe obesity (i.e. $BMI \ge 120\%$ of the 95th percentile1). Clinically relevant cut-points of severe obesity based on total, trunk, and visceral body fat will be established among this diverse cohort of adolescents.

Power analysis

Objective 1:

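### The Year 2 window does not enforce the consistent-season rule, and the gated single term/holiday covariate, with no adjustment for follow-up length, is an unreliable safeguard

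*Combined protocol and SAP*

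**What the plan says.** All references are to the combined protocol and SAP.

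- **Study Design, reason for the rule.** The investigators report having seen that "children's physical activity and other health behaviors vary throughout the year based on school term versus school holiday".
- **Study Design, the rule.** It follows that "each child's Year 0 and Year 2 clinic visits will be scheduled at a consistent time of year". Enrolment is spread deliberately: "we will use a scheduled enrollment to ensure that clinic visits are representative of both school term and school holidays".
- **Study Design, the window.** "Participants will return to clinic approximately 2 years (+/- 6 months) after their Year 0 visit for a Year 2 visit". Accelerometers are worn in the week after Orientation for Year 0. For Year 2 they are collected about 10 days before the visit.
- **Retention.** "Offering assessments during summer and school holidays will increase the likelihood of participation".
- **Statistical Analysis, Objectives 1, 2 and 3.** School term versus holiday "will be considered as an additional covariate if time of year is significantly associated with the independent and dependent variables". Neither the significance level nor the visit whose season is meant is stated. The fixed covariates for Objectives 1 and 2 are age, sex, dietary intake and race.
- **Power analysis.** The primary outcome for Objective 1 is the Year 2 minus Year 0 change in sedentary minutes, compared between severely obese (SO) and not severely obese (NSO) children. Objective 2 relates total fat accumulation to the same change. Its high and low fat gainers are split on the difference in total body fat between the two visits.

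**The concern.** Three gaps meet in the same outcome.

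1. The only numerical limit on Year 2 timing does not protect the seasonal match that the plan wants. A January Year 0 visit and a July Year 2 visit satisfy the window while breaking the scheduling rule. Nothing says how close is close enough, or how to treat a pair that does not match.
2. The statistical safeguard is a single flag behind two significance tests. In a change score, a stable seasonal effect cancels for term-term and holiday-holiday children. It remains, with opposite signs, for term-holiday and holiday-term children. One flag does not separate these four cases.
3. Months between visits is not a listed covariate, although follow-up may differ by 12 months between children.

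A term-to-holiday switch goes straight into the change in sedentary minutes. If switching is equally common in the groups compared, it adds noise. If it differs between them, it biases the contrast. Interval length is a sharper problem for Objective 2, because a longer interval can raise both the fat difference that defines the exposure and the behaviour change that is the outcome.

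**Working it through.** **Inputs from the documents.** Window 24 ± 6 months. Table 5: difference 24 min/day, SD of change 69.6, minimum N 266, α = 0.05, power 80%. About half the sample severely obese. Cap 345, dropout 25%.

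**Assumptions, because the documents give no figure.** Seasonal effect on change 0 to 60 min/day; 25% of NSO children with the season indicator positive; SO share 0 to 20 points higher; both gate tests two-sided at 0.05.

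**Step 1: the plan's own figure.** Per group, n ≈ 2(1.96 + 0.84)² × 69.6²/24² ≈ 132, or 133 with the t correction. Two groups give 266, as in Table 5.

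**Step 2: the window.** 24 − 6 = 18 months and 24 + 6 = 30 months. Counting forward 18 to 30 months from any baseline month reaches all 12 calendar months. Both ends lie six months out of season.

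**Step 3: how often the gate opens.** Completers: 345 × 0.75 = 258.75, taken as 258, split 1:1. Change was generated as 24 × SO + effect × indicator + noise with SD 69.6, in 10,000 data sets per setting. The covariate enters only if the indicator is significant against both obesity group and change. Average bias if season is left out = imbalance × effect.

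Each cell shows the chance of entry, then the bias in min/day if omitted.

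| SO minus NSO share | Effect 15 | Effect 30 | Effect 60 |
|---|---|---|---|
| 0 points | 1.4%; 0 | 4.3%; 0 | 5.0%; 0 |
| 5 points | 6.6%; 0.75 | 13.9%; 1.5 | 14.5%; 3 |
| 10 points | 21.6%; 1.5 | 39.9%; 3 | 43.1%; 6 |
| 15 points | 40.0%; 2.25 | 70.3%; 4.5 | 74.1%; 9 |
| 20 points | 55.3%; 3 | 89.8%; 6 | 92.7%; 12 |

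In the 5 and 10 point rows, omission runs from 1 − 0.431 = 57% to 1 − 0.066 = 93%. Two cautions apply. The bias is the average if season were always left out; data sets in which the gate stays shut tend to have a smaller observed imbalance. Against that, the simulation tests the very indicator that drives the outcome, whereas the plan does not say which visit's season is tested.

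**Step 4: a ceiling for noise.** If Year 2 season were independent of Year 0 season, the share of children switching would be 2p(1 − p), where p is the holiday share. p = 12/52 gives 35.5% and p = 0.5 gives 50%. The added variance is D² × share, where D is the seasonal effect:

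- D = 30, 35.5% switching: √(69.6² + 319) = 71.9.
- D = 60, 50% switching: √(69.6² + 1800) = 81.5.

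With 266 children, power for 24 min/day falls from 80% to about 77% and 67%. With 10% switching, the SD is √(69.6² + 90) = 70.2 to √(69.6² + 360) = 72.1.

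**Step 5: follow-up length.** 30/18 = 1.67. At the same constant rate of fat gain, a child seen at 30 months shows 1.67 times the raw difference of a child seen at 18 months. The later child is therefore more likely to be classed as a high fat gainer, and has also had longer for behaviour to change.

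**The case against.** The strongest reply is that the two scheduling statements operate together: the window is an outer limit and the consistent-season rule applies inside it. That stands. A reader might infer that the plan permits January-to-July pairs, or that they will be common. The documents support neither. A large date shift can also remain term-to-term. What is missing is a tolerance and a rule for mismatches.

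Second, requiring association with exposure and outcome resembles the definition of a confounder, so the gate should open when bias is large. That stands in part. A reader might infer that the covariate will rarely be entered, or that the bias is 6 to 12 min/day. The first holds only when season is unrelated, or weakly related, to the exposure. The second needs a 20-point imbalance with an effect of 30 to 60 min/day, where the gate opens in about 90% to 93% of data sets. The exposed range is the modest imbalance, which two tests often miss.

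Third, the switching rates of 35% to 50% assume no adherence to the scheduling rule, so they are a ceiling. Table 5's SD may also already contain seasonal variation. Both points stand.

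Fourth, a reader might infer from the Retention section that Year 2 visits will drift towards holidays. Holiday slots are also needed to match children enrolled in holidays, and the section does not say that term-baseline children will be moved.

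Finally, this version is dated 3/1/2021, Study Design places Year 2 in 2018-19, and the COVID-19 Survey section refers to participants who have already completed Year 2. A new scheduling rule would come largely too late. The analysis can still be changed.

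**Conclusion.** The point holds as an unreconciled design statement and a weak analysis rule. It does not show that the primary result will be biased.

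- The window spans the whole calendar year and cannot by itself deliver the consistent-season rule. The two statements must be reconciled.
- The gated covariate is the wrong variable for a change score and is admitted on the wrong basis. With season unrelated to severe obesity, its omission costs precision. With a modest imbalance, it will often be omitted while some bias remains, up to a quarter of the 24 min/day target (6/24) at the top of the assumed range.
- The missing interval covariate does not depend on any seasonal assumption. It matters most for Objective 2, because exposure and outcome accumulate over the same months.

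The seasonal effect, imbalance and holiday share are all assumed, so the sizes are a range and not a forecast. The case for change rests on the low cost of a better prespecified model.

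**What to change.** In the Objective 1 and Objective 2 change models:

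- Delete the significance condition on school term versus holiday.
- Always include the child's Year 0-to-Year 2 school-status pair (term-term, term-holiday, holiday-term, holiday-holiday), defined by the accelerometer weeks and not by the clinic dates.
- Always include the months between visits.

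In Study Design, reconcile the window with the consistent-season rule and state how a mismatched pair is handled. For any visits still to be scheduled, match Year 2 school status to Year 0 where possible, and flag mismatches without discarding them.

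The inputs are device and visit dates and the school calendar. The cost is three degrees of freedom for the pair and one for the interval if entered linearly, with about 258 expected completers. No child is lost from the analysis.

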We focus on severe obesity, the fastest growing sub-category of obesity7,14 affecting between 4% and 6% of youth in the U.S.15 This group of children is at highest risk for medical complications including heart disease, type 2 diabetes, and cancer.15 Our research team, among others, has identified the importance of physical activity and low levels of sedentary behavior for children's health outcomes. In 2010-11, our research team conducted the WAIST study, which was a cross-sectional examination of 423 children and adolescents aged 5 to 18 years that were evenly distributed by age, sex, race (African American or White), and obesity status (PI: [name], who is an Investigator on this project). Thus far we have published 8 manuscripts from this cohort.16-23 We demonstrated that engagement in at least 60 minutes/day of physical activity on at least 4 days/week was related to lower body fat and lower visceral adiposity.17 Conversely, sedentary behavior characterized by TV viewing was related to higher visceral adiposity and cardiovascular risk.18 Indeed, 24% of the WAIST cohort already had at least 2 cardiometabolic risk factors at baseline (elevations in waist circumference, blood pressure, triglycerides, or fasting glucose, or low levels of high density lipoprotein cholesterol). The present project will build upon our prior work by investigating these relationships among adolescents who are classified as severely obese.

Although behavior modification that employs physical activity is considered the first-line treatment for severe obesity,¹⁵ we know very little about current patterns of physical activity or the barriers and facilitators of physical activity among children with severe obesity. A scientific statement from the American Heart Association in 2013 issued an appeal for innovative behavior-based treatment and minimally invasive procedures to treat severe obesity in children and adolescents.¹⁵ Few lifestyle modification studies have focused on children with severe obesity, and interventions that do include this population have not taken into account environmental or socio-emotional factors related to children's health behaviors. Family-based behavioral treatment that employs physical activity, dietary counseling, and behavioral strategies to implement and sustain changes have had limited long-term success,24-27 with many children returning to baseline weight following the completion of the intervention.^{24,25,28}

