BMIz- BMI percentile and BMIz will be calculated based on the participant's age, height, and weight using the CDC 2000 growth charts.⁶¹ Severe obesity will be categorized as $\geq 120\%$ of the 95th BMI percentile.¹⁵

Waist circumference - will be measured at the natural waist (halfway between inferior border of rib cage and superior aspect of iliac crest) with clothing moved out of the way.

Body composition

DXA- Total body fat and trunk fat will be assessed by whole-body DXA using a GE iDXA scanner (GE Medical Systems, Milwaukee, WI) to quantify total and regional body fat (including trunk fat).

DXA Instructions given to participant: This scan measures the amount of bone, muscle, and fat in your body. The scan will be performed using a whole-body scanner. You will be required to wear a hospital gown, to remove all metal-containing objects from your body, and to lie down on the table. You will be carefully positioned on the table, and your legs will be placed together using two Velcro straps. A scanner emitting low energy X-rays and a detector will pass along your body. You will be asked to remain completely still while the scan is in progress. The scan takes approximately ten minutes.

MRI - Visceral fat, i.e. visceral adipose tissue, will be assessed by water-fat shifting MRI using the General Electric Discovery 750w 3.0 Tesla (GE Medical Systems, Milwaukee, WI). IDEAL-IQ imaging technique will be used to generate water-only, fat-only, in-phase, and out-of-phase echoes in a single acquisition with a 20-second breath-hold. For female subjects ages 12 and above or females under the age of 12 who are menstruating as verbally confirmed by a parent or legal guardian, a negative urine pregnancy test will be required prior to DXA or MRI scans.

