A fasting sample of blood will be taken by a trained phlebotomist following standardized clinic procedures. The participant will be offered EMLA cream (lidocaine 2.5% and prilocaine 2.5%) to minimize pain related to blood draws. Serum concentrations of glucose, triglycerides, low density lipoprotein cholesterol (LDL-C), and high density lipoprotein cholesterol (HDL-C) will be obtained from a DXC600 manufactured by Beckman Coulter. Serum CRP levels are determined by immunoassay with chemiluminescent detection, run on an Immulite 2000 manufactured by Siemens. Insulin will be assayed on the Siemens Immulite 2000. Approximately two teaspoons of blood will be collected.

An aliquot of whole blood and aliquot of serum will be stored in case further tests are needed and if further consent is obtained from the subject.

Cardiometabolic risk factors

Resting blood pressure – will be assessed using standard clinical procedures on a standard sphygmomanometer.₆₂

Cardiometabolic risk factors - Elevated cardiometabolic risk (i.e. metabolic syndrome) will be categorized as the presence of three or more cardiometabolic risk factors using the established criteria in the 2011 National Institutes of Health Guidelines for Cardiovascular Health and Risk Reduction in Children and Adolescents.₆₃

24-hour Dietary Recall (ASA-24)

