The primary outcome for the first objective is change in minutes of sedentary behavior between Year 0 and Year 2 (i.e. Year 2 values minus Year 0 values). Baseline estimates for the two groups were calculated using the WAIST cohort data (from the 2010-11 assessment). Based on data from Berkey et al.,75 the SO group is assumed to increase their sedentary time by 30 minutes/day at year 2, while smaller increases in sedentary time is expected for the NSO group (**Table 5**). A minimum of 334 participants is needed to ensure a well-powered study with significance level of $\alpha = 0.05$, 80% power to detect a 24 minute difference change in sedentary behavior between the two groups, and allowing for a dropout rate of 25%. Therefore, our sample size of up to 345 participants will be sufficient.

Change in minutes/day of sedentary time for NSO group	Change in minutes/day of sedentary time for SO group	Difference in change between groups	Standard deviation of change between groups	Minimum sample size	Total sample size (allows for 25% dropout)
2.4	30.0	27.6	69.6	202	253
3.6	30.0	26.4	69.6	222	278
4.8	30.0	25.2	69.6	242	303
6.0	30.0	24.0	69.6	266	334

Table 5. Difference in changes in sedentary time based on severe obesity status. *Note.* NSO is the group classified as not severely obese; SO is the group classified as severely obese.

Note. NSO is the group classified as not severely obese; SO is the group classified as severely obese.

Secondary analyses will include change in daily MVPA minutes between years and change in days/week of physical activity (\geq 60 minutes MVPA/day) between years. Power analysis was conducted on these outcomes, using the WAIST cohort and data from Nigg et al.,76 and our sample size will have power of 93.8% and 90.4% to detect a significant difference in change in daily MVPA minutes and change in days/week of physical activity, respectively.

Contingencies

Based on national reference data, it is possible that very few or no severely obese children meet the healthy behavior or cardiometabolic health criteria (e.g. no severely obese child attains ≥ 60 minutes of MVPA/day; no severely obese child has a waist circumference < 90th percentile). If this is the case, the dichotomous dependent variable will be adjusted to be quartiles, so that the analyses is interpreted as the likelihood of a severely obese child being in the top (healthiest) quartile of the health behavior or cardiometabolic health criteria for the overall cohort.

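### Elevated cardiometabolic risk appears to count waist circumference while BMIz is the exposure, so the Objective 1 odds ratio is biased upward and no waist-excluded analysis is planned

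*Combined protocol and SAP*

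**What the plan says.** All references are to the combined protocol and SAP.

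- **Outcome.** Under Cardiometabolic risk factors: "Elevated cardiometabolic risk (i.e. metabolic syndrome) will be categorized as the presence of three or more cardiometabolic risk factors". The criteria are taken from a cited external guideline, and the components are not listed there.
- **Components.** The Background section on the impact of severe obesity describes the factors the team counted in its earlier WAIST cohort: "elevations in waist circumference, blood pressure, triglycerides, or fasting glucose, or low levels of high density lipoprotein cholesterol". That makes five, with waist first. The Contingencies paragraph for Objective 1 (Power analysis) treats a waist below the 90th percentile as a cardiometabolic health criterion in the present study.
- **Exposure.** Statistical Analysis, Objective 1: "logistic regression models will be used to determine the association between BMIz with the likelihood of not meeting recommended behaviors" or "being at elevated cardiometabolic risk". The exposure written for this outcome is BMIz. The SO versus NSO logistic step that follows lists changes in sedentary time, MVPA and continuous risk factors, and does not list the elevated-risk category. However, the lead sentence for Objective 1 names severe obesity as the independent variable, and the contingency words the dichotomous analysis as the likelihood for a severely obese child.
- **Saturation.** The same contingency gives as a possibility that "no severely obese child has a waist circumference < 90th percentile". The planned response is that "the dichotomous dependent variable will be adjusted to be quartiles", read as the chance of being in the healthiest quartile.

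No section removes waist from the count or plans a version without it.

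**The concern.** BMIz, severe obesity and waist circumference all measure adiposity. If waist is one of the factors counted towards three, a child with high BMIz usually starts with one factor already met and needs two more, whereas a child with a normal waist needs three of the other four. The odds ratio then mixes two things: any relation of obesity to blood pressure, triglycerides, HDL and glucose, and the near-automatic relation of BMIz to waist.

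Hypothesis 1.A concerns the association of severe obesity with cardiometabolic risk factors. Readers would take an odds ratio above 1 as evidence about blood pressure, lipids and glucose. Under the plan as written, such a result is expected even if none of those four differed by obesity status.

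**Working it through.** The documents give no prevalence, power or odds ratio for elevated risk, so there is no stated figure to reproduce. The check asks what odds ratio the definition produces when obesity has no relation to the four non-waist factors.

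**Inputs**
- Three or more factors define elevated risk (Cardiometabolic risk factors).
- Five factors including waist (Background list for the WAIST cohort, supported for waist by the Objective 1 contingency). The count of five is an inference.
- High waist in SO: w1 = 1.0, the extreme that the contingency allows for.
- High waist in NSO: w0 = 0.2 to 0.5. Assumed.
- Prevalence q of each other factor: 0.10 to 0.30, the same in SO and NSO, factors independent. Assumed.

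**Formula**

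Let X be the number of the other four factors present, X ~ Binomial(4, q). Then

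P(elevated) = w·P(X≥2) + (1−w)·P(X≥3) = P(X≥3) + w·P(X=2).

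The odds ratio compares this at w1 with this at w0.

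**Results with w1 = 1.0**

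| q | P(elevated), SO | w0 | P(elevated), NSO | OR |
|---|---|---|---|---|
| 0.10 | 0.0523 | 0.20 | 0.0134 | 4.06 |
| 0.10 | 0.0523 | 0.50 | 0.0280 | 1.92 |
| 0.15 | 0.1095 | 0.30 | 0.0412 | 2.86 |
| 0.20 | 0.1808 | 0.35 | 0.0810 | 2.51 |
| 0.20 | 0.1808 | 0.50 | 0.1040 | 1.90 |
| 0.30 | 0.3483 | 0.20 | 0.1366 | 3.38 |
| 0.30 | 0.3483 | 0.50 | 0.2160 | 1.94 |

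Worked row (q = 0.20, w0 = 0.35): P(X≥2) = 0.1808 and P(X≥3) = 0.0272. NSO: 0.35 × 0.1808 + 0.65 × 0.0272 = 0.0810. OR = (0.1808/0.8192) / (0.0810/0.9190) = 0.2207/0.0881 = 2.5.

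Over the assumed grid the range is 1.90 to 4.06. Wider assumptions (q = 0.08-0.25, w1 = 0.95-1.0, w0 = 0.1-0.7) give 1.34 to 6.85, always above 1.

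**Anchor in the documents.** The Background reports that 24% of the WAIST cohort had at least two factors. Solving w·P(X≥1) + (1−w)·P(X≥2) = 0.24 gives q = 0.19, 0.16, 0.14, 0.12 and 0.11 for an assumed high-waist prevalence w of 0.2, 0.3, 0.4, 0.5 and 0.6. These values lie within the assumed 10-30%.

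**Chance of a nominally significant result.** 345 × 0.75 = 258.75, so about 129 per group at a 1:1 split. With q = 0.15 and w0 = 0.30 (11.0% versus 4.1%), the chance of two-sided p < 0.05 is about 55%, although no metabolic factor differs.

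**BMIz as exposure.** The same formula applies with w as a function of BMIz: P(elevated | BMIz) = P(X≥3) + w(BMIz)·P(X=2). If high waist becomes more common as BMIz rises, so does P(elevated), with q held fixed. The direction therefore carries over to the model actually written. The size per BMIz unit depends on the BMIz distribution and the waist-BMIz relation, which the documents do not give.

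**With waist removed.** If the outcome is two or more of the other four, both groups have P(X≥2) and the OR is 1.00. The excess comes entirely from the waist component.

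**The case against.** The strongest points on the other side are these.

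1. *The definition is an established one.* Asking whether obesity is associated with metabolic syndrome as usually defined is a legitimate descriptive question. This stands, and it is why the standard outcome should be kept.
2. *The plan models each risk factor separately.* It does, and those non-waist models do not share the overlap. But they are written for change between visits, so they only partly answer what the elevated-risk model is meant to answer.
3. *The plan foresees saturation and switches to quartiles.* That deals with an empty cell. Waist stays in the criterion, so the overlap remains.
4. *The size rests on assumptions.* It does. High waist in NSO, component prevalence, independence and 100% high waist in SO are not figures from the documents. The direction does not depend on the particular values.

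A reader might go further and infer that the odds ratio for severe obesity must exceed 1 by construction. The documents do not support that. A severely obese child still needs two further factors. With w1 = 1.0, q = 0.10-0.25 and w0 = 0.2-0.5, the odds ratio returns to 1 if the other factors are about 0.5 to 0.7 times as common in SO as in NSO. In five simulated no-association cases, the sample odds ratio was at or below 1 in about 0.5% to 10% of samples. Also, the exposure written for this outcome is BMIz, the component list is inferred from two other sections, and saturation of waist is stated as a possibility.

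**Conclusion.** The concern holds as an upward bias. Elevated risk appears to count waist, BMIz is the exposure, and no waist-excluded version is planned. If the other four factors are unrelated to obesity, the expected SO versus NSO odds ratio is 1.9 to 4.1 instead of 1. This assumes independent factors at 10-30% in both groups, and high waist in 100% of SO and 20-50% of NSO. The direction, though not the size, needs only that waist is counted and that high waist is more common at higher BMIz.

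The reach is limited. Change in sedentary time (the Objective 1 primary outcome) and the continuous models for factors other than waist are not affected. Neither is Objective 2, where elevated risk is not an outcome.

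**What to change.** For the Objective 1 elevated-risk models:

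- List the components and thresholds that make up the count, and state whether the exposure is BMIz, SO versus NSO, or both.
- Prespecify a waist-excluded outcome, for example two or more of blood pressure, triglycerides, HDL and glucose, and report it alongside the standard definition.
- State that any conclusion that obesity raises metabolic risk rests on the waist-excluded result.
- If the quartile contingency is used for the cardiometabolic criterion, apply the same exclusion there.

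The cost is one derived variable from measurements already scheduled at both visits. The downside is a non-standard count that is less comparable with published prevalence; reporting the standard definition beside it covers that.
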